10. HUMAN SUBJECTS PROTECTION

10.1. Subject Selection

10.1.1. Statement of equitability

Subjects in this study will all be recruited within the vicinity of each of the sites by the site teams. We expect that the racial and sexual distributions of patients enrolled in this study will reflect those of the general population in each region. All of the sites have experience recruiting minorities through a concentrated effort in communities that have high representation of ethnic and racial minorities and through advertisements in newspapers and radio stations whose readers/listeners are predominantly of specific racial or ethnic minorities.

10.1.2. Justification for exclusion of children

Children (those under age 21) will not be included in this study because insufficient data are available with CERC-501 in adults to judge potential risk in children.

10.1.3. Justification for exclusion of other vulnerable subjects

Because the aims of this study can be achieved with individuals who are not members of vulnerable groups (those who lack capacity for consent, prisoners, pregnant women etc.), we will not have to include any vulnerable subjects.

10.1.4. Safeguards for vulnerable populations

In order to protect vulnerable populations, they will be excluded from participation in this study. This includes pregnant women. In order to identify women who are pregnant, all women of childbearing potential will undergo a blood pregnancy test and it must be negative before subjects can continue in this study. If sexually active, female subjects must agree to use appropriate contraceptive measures for the duration of the study and for 1 month afterwards. Medically acceptable contraceptives include: (1) surgical sterilization (such as a tubal ligation or hysterectomy), (2) approved hormonal contraceptives (such as birth control pills, patches, implants or injections), (3) barrier methods (such as a condom or diaphragm) used with a spermicide, or (4) an intrauterine device (IUD). Contraceptive measures such as Plan B (TM), sold for emergency use after unprotected sex, are not acceptable methods for routine use. If subjects do become pregnant during this study or if they have unprotected sex, they will be instructed to inform the study physician immediately.

Participation of sexually active men has the potential to damage sperm, which could cause harm to a child that a subject might father while on this study. As a result, in order to protect subjects, sexually active male subjects will have to agree to use a medically acceptable form of birth control during and 1 month after this study in order to participate. Medically acceptable contraceptives include: (1) surgical sterilization (such as a vasectomy), or (2) a condom used with a spermicide. Contraceptive measures such as Plan B (TM), sold for emergency use after unprotected sex, are not acceptable methods for routine use. Subjects will be instructed to inform their partners of the potential for harm to an unborn child and that they should immediately inform the study doctor if pregnancy occurs.

10.1.5. Qualifications of Investigators

The overall principal investigator for this study is [name], MD, MS. He is highly experienced in serving as the principal investigator for single-site and multi-site clinical trials with patients with mood and anxiety spectrum disorders. This includes those employing fMRI scanning as will be carried out in the current study. Each one of the site PIs was selected because they too are highly experienced in serving as PIs for studies of patients with mood and anxiety spectrum disorders and they themselves or those at their site also have experience and expertise in carrying out the assessments that will be carried out in this study.

11. ANTICIPATED BENEFIT

Subjects may not receive any direct benefit from participating in this study. There is a small possibility that we may detect an unrelated medical condition during the procedures conducted in this study which could have health benefits for some individuals. Some individuals may experience improvement in their symptoms through participation in the study, though some are likely to remain the same or get worse. However, the drug will not be available to subjects after the study concludes. The information that we get from this study may help us to better treat future patients with mood and anxiety disorders.

The available treatments for patients with mood and anxiety spectrum disorders have significant limitations. This study has the potential to take steps to address these

limitations by: 1) testing a promising new treatment for mood and anxiety spectrum disorders; 2) evaluating a potential target in the brain which could serve as the basis for development of additional new candidate compounds for the treatment of patients with mood and anxiety spectrum disorders; 3) establishing more expeditious methods for evaluating potential new therapies for patients with mood and anxiety spectrum disorders; and 4) specifically establishing methods for the development of new therapies targeting anhedonia, an important endpoint.

12. CLASSIFICATION OF RISK (for the study as a whole)

12.1. Risk Classification

This study is associated with more than minimal risk

12.2. Overall Risk and Benefit Consideration

The risks of the study are reasonable in relation to the anticipated benefit described in Section 11.

13. CONSENT DOCUMENTS AND PROCESS

13.1. Consent Procedures

All participants will receive a verbal explanation in terms suited to their comprehension of the purposes, procedures and potential risks of the study and of their rights as research participants. Participants will have the opportunity to carefully review the written consent form and ask questions regarding this study prior to signing.

14. DATA AND SAFETY MONITORING

14.1. Data and Safety Monitor

Data and safety will be monitored by the NIMH Data and Safety Monitoring Board (DSMB). The NIMH DSMB functions include, among many, the assessment of interim data to determine whether the treatment interventions show a clear risk when compared with placebo. The main purpose of the NIMH DSMB is to assess safety of the interventions by determining whether an increased number of adverse events occur among study participants receiving the intervention compared to the participants receiving placebo treatment. Data will be reviewed every 4 months after the NIMH DSMB approval of the protocol and consent form.

14.2. Data and Safety Monitoring Plan

As described above, an independent DSMB will be established by NIMH that will meet regularly to review trial data in order to protect subject safety and data integrity. The

DSMB will meet prior to the start of the study to review the protocol and consent form. After the study commences, the DSMB will meet at least every 4 months.

Prior to each DSMB meeting that takes place after the study commences, the Principal Investigator will generate and circulate a full report to the NIMH DSMB members and the study biostatistician, summarizing recruitment, patient status and safety data for the study to be reviewed at that DSMB meeting including SAE reports. These reports will be prepared illustrating patient status and safety data. Patient status reports will summarize the number of subjects screened, eligible, randomized, treated, and completing the study -- by month and overall to-date. Detailed tables will be provided on reasons for ineligibility, and reasons for early termination of enrolled subjects. Safety reports will include summary data on all subjects experiencing the emergence or worsening of any adverse event (including abnormal laboratory values) during the course of a study, and during each study phase (screening, treatment, follow-up) -- each relative to the number of subjects in that phase. More detailed reports will provide information on the specific types of adverse events experienced, and the number that constituted Serious Adverse Events (SAEs) or led to termination from the study. Details of all SAEs occurring during a study will be provided to the DSMB for review of the nature and outcome of each SAE, as well as that all appropriate follow-up and required reporting was done in a timely manner. Tabulation and descriptions for protocol deviations will also be included in the report.

In addition to reviewing these data, the DSMB will also review procedures for ensuring that data are collected and analyzed per protocol privacy and that subject confidentiality is being maintained.

The DSMB will also carry out an overall assessment of the risk-benefit ratio of the study based on the available data. If there is a concern that the risks might outweigh the benefits, then enrollment will be suspended pending a more detailed review. However, if it is clear that the risks outweigh the benefits, then they will recommend permanently stopping the study.

15. QUALITY ASSURANCE

15.1. Program Management Committee

The Program Management Committee (PMC) will have primary responsibility for Quality Assurance Monitoring for this study. This committee will be chaired by the DCRI Project Leader and Co-Chaired by the FAST-MAS PI, [name], MS. This committee will also include several teams: 1) Site Management – this includes a Clinical Research Associate (CRA), who, along with the Project Lead will have primary site management responsibility; 2) Data Management – this includes the Lead Biostatistician, and the Program Manager of electronic data system (EDC) and data management group; 3) Assessment/Signal Detection – [name]. will lead oversight of assessments and quality of data collection; 4) Magnetic Resonance Imaging (MRI) – [name]. will lead oversight for ensuring the quality of MRI methods, MRI data collection, and MRI data analysis.

15.2. Quality Assurance Plan

The PMC will meet regularly via teleconference (weekly from the beginning of study start up until the end of the study) to provide operational leadership to ensure that the study is implemented and managed efficiently and effectively and to oversee Quality Assurance. In this effort, they will work collaboratively with the NIMH Program Team. The Quality Assurance Plan includes the PMC carrying out the following key activities.

15.2.1. Monitoring and Managing Study Timelines

One of the most important responsibilities of the PMC will be to monitor study timelines by assessing whether key timeline milestones are being met by each of the sites. The PMC will be responsible for collecting ongoing data on whether milestones are being met. [name] will then lead forming a strategy to address problems in meeting recruiting or other milestones and will work directly with the site PI in the implementation of that strategy.

15.2.2. Monitoring for Protocol Deviations

Another important function of the PMC will be to monitor for protocol deviations. These will be identified via review of electronic case report by the Site Management and Data Management teams. In addition each site will report all protocol deviations to the Site Management team. The PMC will monitor the protocol deviations and institute plans for addressing ongoing problems/deficiencies where needed.

15.2.3. Site Training

Site Training will take place in a number of steps. This will include training from the Site Management team on many study procedures, training from [name] on completing subject assessments, training from [name] on MRI procedures, and EDC training (see following section). The procedures to be carried out at the sites will be reviewed. This will also be the case for requirements for training of staff and documentation that those carrying out tasks for this study have the appropriate training documented.

[name] will implement processes that he and his group have developed for rater training and data quality review to promote the collection of high quality data. These processes will be employed in this FAST-MAS study and are outlined below:

- a. Develop a protocol-specific guide for the MINI, HAM-D, HAM-A and C-SSRS.
- b. Provide all testing materials to the sites.
- c. Pre-screen 2 raters per site, including assessing the sites for their rater training/credentials, extent of rater experience, and experience with clinical populations, and experience with the specific instruments used in this study.
- d. Implement training procedures, including preparations for training, sending protocol-specific procedures, and providing access to clinical rating training videos for raters to review prior to the investigator's meetings.
- e. Individual certification of at least one rater per site.
- f. Review of testing procedures by [name] via a presentation to the site investigators.
- g. Either in-person or phone training and certification for all raters.

15.2.4. Site Electronic Data Capture (EDC) System Training

The Data Management team will conduct a web-based training on the EDC systems for site personnel. The site teams will enter data in the training environment during the training session, ask questions, and receive feedback on their work. In addition to the training session, the Data Management team will be available on a continuing basis to assist site personnel over the phone with questions related to remote data entry. Throughout the trial, for new study coordinators training will be delivered via a webbased program and telephone.

15.2.5. Research Ethics Training

The CC will ensure that all faculty, clinical staff having direct patient contact, and all personnel involved in site and data management involved in this study will meet human subjects training requirements.

15.2.6. Ongoing Site Management/Monitoring

Ongoing Management/Monitoring of each site will be carried out by the DCRI Site Management team which consists of the DCRI Project Leader, and a Clinical Research Associate (CRA). Site Management will include both on-site and in-house monitoring, routine communication with the site personnel, and collection of site-related data and documents. A particular focus will be to work with the site on effective recruiting strategies. The CRA will also provide ongoing monitoring of the recruitment at the site and report this to the FAST-MAS PI along with suggestions for improving enrollment. The CRA will carry out the same type of monitoring and trouble-shooting with protocol implementation and quality of adherence to study procedures. [name] and the Signal Detection team will also play an important role in ongoing monitoring in order to maintain high quality in study assessments. Their activities will include:

- a. Monitoring frequency of assessments carried out by raters.
- b. Raters not administering assessments for 4 months will be required to complete refresher training.
- c. Carrying out a phone certification process for replacement raters when there is site rater turnover.
- d. Participate in biweekly conference calls to prepare for training meetings, review data collection processes, and address all study-related assessment issues as they arise over the course of the study.

16. ADVERSE EVENT AND UNANTICIPATED PROBLEM REPORTING

All adverse events serious and non-serious, expected and unexpected, related and unrelated to study drug will be documented and reported to the sponsor.

16.1. Plan for Assessment for Adverse Events

The Principal Investigator or a Co-Investigator at each site will monitor all subjects for adverse effects from the time of signature on the informed consent throughout their participation in the study. This will include carrying out a clinical interview for adverse events at each visit and administering the Patient Reported Inventory of Side Effects (PRISE). In addition, a series of safety assessments will be carried out and the findings reviewed by the site PI or Co-I. These safety assessments will include: the Columbia Suicide Severity Rating Scale (CSSRS) (Posner, 2011), vital signs (height, weight, blood pressure, and pulse), physical examination, Beta-HCG serum pregnancy test, urine drug screen, complete blood count with differential, electrolytes, comprehensive metabolic panel including liver function tests, thyroid function tests, urinalysis, the Clinical Global Impression - Improvement (CGI-I), the Clinical Global Impression - Severity (CGI-S) and ECG and EEG (obtained at baseline, at the end of 8 weeks of daily treatment with study drug). In addition, because gastritis was noted in some of the rats administered CERC-501 and some gastric-related side-effects were observed in the Phase 1 human studies, specific assessment for gastric adverse events will be carried out in this study. This will consist of collecting blood at baseline, 4 weeks, and 8 weeks of double-blind treatment from which gastrin and pepsinogen I/II levels will be determined.

These data will be used to assess for adverse event type, severity, expectedness, and causal relationship to study drug as defined below.

16.1.1. Adverse Events

An adverse event (AE) is defined as any untoward medical occurrence associated with the use of the study drug in a subject whether or not considered drug related. An AE can therefore be any unfavorable and unintended sign, symptom or disease temporally associated with the use of the drug. Any change in clinical status, ECGs, laboratory tests, physical examinations, etc., that is considered clinically significant by the site investigators.

16.1.2. Serious Adverse Events (SAE)

An SAE is any adverse event where any of the following is the case:

- Is associated with death.
- Is life-threatening: Places the subject at immediate risk of death at the time of the event as it occurred. This includes suicide attempts. It does not include an AE that, had it occurred in a more severe form, might have caused death.
- Causes persistent or significant incapacity or substantial disruption of the ability to conduct normal life functions.
- Is associated with inpatient hospitalization or prolongation of hospitalization.
- Is associated with a congenital anomaly or birth defect.
- Important medical events that may not result in death, be life threatening, or require hospitalization may be considered a serious adverse event when, based upon appropriate medical judgment, they may jeopardize the subject and may require medical or surgical intervention to prevent one of the outcomes listed in this definition above. This determination is based on the opinion of either the investigator or sponsor (e.g., if either believes it is serious, it must be considered serious).

16.1.3. Assessment of Adverse Event Severity

The determination of adverse event severity will be made by the site PI or site Co-I. The severity of AEs will be graded using the following definitions:

- **Mild:** Participant is aware of symptoms or has minor findings, but tolerates them well and no or minimal intervention is required
- **Moderate**: Participant experiences enough symptoms or findings to require intervention
- Severe: Participant experiences symptoms or findings that require significant intervention or is life threatening (participant is at immediate risk of death from symptoms or findings that require aggressive medical management)

16.1.4. Assessment of Causal Relationship to Study Drug

The site PI or Co-Investigator will rate the causal relationship of any adverse event to the study drug using the following:

- Not related: There is not a reasonable causal relationship to the investigational product and the adverse event
- Unlikely related: An AE that has some possibility of being related to the study drug but this possibility is remote.
- **Possibly related**: An AE that has little or no relationship to the study drug and there exists a more likely alternative cause
- **Probably related**: An AE that is likely to be related to the administration of the study drug and an alternative cause less likely when compared to the study drug
- **Definitely Related**: An AE that has a strong temporal relationship to the study drug. AE will recur with continued or repeated use of the study drug, and another cause is unlikely or less likely

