16.2. Documentation of Adverse Events

All events determined to be an AE, based on physical examination, laboratory findings, or other means, will be recorded. Each AE will be entered into the electronic data capture (EDC) system by the site PI or qualified designee. The investigator will provide date of onset and resolution, assessment of severity, intensity, and frequency, action(s) taken, changes in study drug dosing, relationship to study drug, and outcome. When additional relevant information related to an AE becomes available, the site PI or Co-I will record follow-up information according to the same process used for reporting the initial event as described above. They will follow all Adverse Events until resolution or they no longer believe that it is clinically significant. AEs ongoing at the time of the last dose of study drug will be followed up for as long as necessary to adequately evaluate the participant's safety, until they are resolved, or until it is determined by the investigator not to be clinically significant. All women of childbearing potential will be instructed to notify the Investigator if they become pregnant at any time during the study or within 30 days of last study evaluation. The pregnancy will be followed until delivery. Any

associated AEs or SAEs that occur to the mother or fetus/child will be recorded in the EDC system.

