16.3. Reporting of Adverse Events

Any SAE entered into the EDC system will generate automatic notification to the DCRI Safety Surveillance Team. The DCRI Safety Surveillance Team will review all SAEs at the time they are reported and immediately report them to the Principal Investigator [name]. [name] or his designee will be responsible for notifying the NIMH Contract Officer's Representative (COR), NIMH DSMB and Cerecor within 1 - 2 business days of receipt of all site reported SAEs. [name] or his designee will be responsible for forwarding written IND Safety reports (for those events identified as serious, related and unexpected) to the NIMH COR, NIMH DSMB, Cerecor, the site PIs, and the Duke IRB within 7 days (fatal/life threatening) and/or 15 days (for all other event determined to meet expedited reporting criteria).

The individual site principal investigators will be responsible for reporting SAEs occurring in subjects at their respective sites to their local Institutional Review Boards (IRB) per local IRB reporting requirements.

[name] or his designee will be responsible for notifying the FDA in a written IND safety report of all SAEs determined to meet expedited reporting criteria within 7 days (for fatal/life threatening events) and/or 15 days (for all other event determined to meet expedited reporting criteria) per 21 CRF 312. 32. Sites will be responsible for submitting IND Safety Reports to their respective IRBs per their local requirements. Documentation will be retained by each investigative site.

Pregnancy occurring during a clinical investigation, although not considered a serious adverse event, must be reported to the DCRI within the same timelines as a serious adverse event. The pregnancy will be recorded on the appropriate pregnancy form and will be followed until final outcome. Any associated AEs or SAEs that occur to the mother or fetus/child will be recorded on the appropriate AE or SAE eCRF form and processed accordingly. The DCRI Safety Group will notify the NIMH COR, NIMH DSMB, and Cerecor of any pregnancy occurring during the study within the same timelines as a serious adverse event. The site principal investigators will be responsible for notifying the respective IRB of any pregnancies occurring at their sites.

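### The definition of Possibly related in Protocol 16.1.4 contradicts its label and leaves an AE with an evenly balanced cause in none of the five causality levels

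*Protocol*

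**What the plan says.** Protocol section 16.1.4 tells the site principal investigator or co-investigator to rate each AE on five levels, in ascending order:

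- Level 1, Not related, is worded as "There is not a reasonable causal relationship to the investigational product and the adverse event".
- Level 2, Unlikely related, covers events for which a drug link is conceivable but judged remote.
- Level 3, Possibly related, is worded as "An AE that has little or no relationship to the study drug and there exists a more likely alternative cause".
- Level 4, Probably related, needs the drug to be the likely cause, with "an alternative cause less likely when compared to the study drug".
- Level 5, Definitely related, needs close timing, recurrence on further use, and the condition that "another cause is unlikely or less likely".

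Section 16.2 makes the rating part of each AE record, which includes "changes in study drug dosing, relationship to study drug, and outcome". Section 16.3 calls for written IND safety reports "for those events identified as serious, related and unexpected", and for reports to the FDA of "all SAEs determined to meet expedited reporting criteria" under a cited federal regulation. Neither statement says which of the five levels count as related.

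**The concern.** A causality scale should rise from one level to the next, and each definition should agree with its label. The third level here does neither. Its label signals a real possibility of a drug effect, while its definition describes a slight or absent connection with a likelier explanation elsewhere. An investigator with an evenly balanced case must choose between the label and the text beneath it, and two careful investigators can choose differently.

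At stake is the consistency of causality coding across six sites and, through the word related, one of three conditions for a written IND safety report. As an illustration only, consider a hospitalization for worsened depression. It would be serious under section 16.1.2, and depression is not among the ten expected events in section 16.1.5. Section 6.4 says the drug might produce depressive symptoms, and section 6.2 says that going without therapy may worsen the enrolled disorder. Causality would then be the remaining condition, and if the investigator thinks the two explanations about equally plausible, the scale has no place for the event.

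**Working it through.** No arithmetic model applies, and the plan states no figure to reproduce. The check sets the definitions side by side and applies each one to test cases.

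**Order of the lowest three levels.** Not related means no reasonable causal link. Unlikely related means some possibility, but a remote one. Possibly related means a slight or absent link together with a likelier alternative. The part of that definition allowing no link falls within Not related. The part allowing a slight link is no stronger than a remote possibility. So the third level does not sit above the second.

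**Test case A: drug possibility more than remote, alternative cause about equally plausible.**

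| Level | Condition that fails |
|---|---|
| Not related | a reasonable causal link exists |
| Unlikely related | the possibility is not remote |
| Possibly related | both: the link is more than slight, and the alternative is not likelier |
| Probably related | the alternative is not less likely than the drug |
| Definitely related | the alternative is neither unlikely nor less likely |

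Result: 0 of 5 levels fit.

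**Test case B: drug possibility more than remote, alternative cause somewhat likelier.** Possibly related is met on the alternative-cause half and fails on the slight-or-absent half. No other level fits.

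**Test case C: drug possibility more than remote but not likely, only weaker alternatives (for example, an unexplained event).** Not related and Unlikely related fail as in case A. Possibly related fails because the link is more than slight and no alternative is likelier. Probably related fails because it also requires the AE to be likely due to the drug. Definitely related fails unless there is a strong temporal relationship and recurrence. This case matters for the fix: a new definition that required an equal or likelier alternative would still leave it out.

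**Search for a correction or a mapping.** No other part of the Protocol restates the five levels. The closing paragraphs of 16.3 put possible relatedness beside relatedness when defining unanticipated problems. That rule covers problems that are not AEs and concerns participation in the research rather than the drug. It shows that the Protocol elsewhere uses the term in its ordinary sense, but it does not sort the five levels into related and unrelated. The available SAP text ends in its background section and says nothing on causality.

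**The case against.** The strongest reply is that the labels and their order make the intent plain. Experienced site investigators would put a middling event under Possibly related whatever the sentence beneath it says, so the gap exists only on a strictly literal reading. Many raters may well do this. But 16.1.4 tells them to rate by the definitions given, and a scale that works only when its text is ignored invites inconsistent coding.

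The second reply is that little depends on the rating, and much of this stands. Section 16 sends all AEs to the sponsor, related or not. Under 16.3 the safety team reviews every SAE, and the NIMH contract representative, the DSMB and the company are notified within 1-2 business days of receipt. Section 14.2 gives the DSMB details of all SAEs. The site rating is not shown to decide any report alone.

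The third reply is that a mapping to related may sit in material not seen here. That is fair. The SAP contents list runs to page 61 while the available text stops at the background, no AE-form instructions are available, and the regulation cited in 16.3 is not reproduced. The missing mapping therefore supports a request for clarification, not a finding of error.

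**Conclusion.** The definition of Possibly related is wrong as written and should be corrected. That rests on the text of 16.1.4 alone and is secure. Its practical size is modest: it affects the consistency of causality coding and possibly the judgment of relatedness for IND safety reports. It does not touch the primary analysis, sample size or error rate, and no available passage plans an analysis by causality.

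A reader might infer more than the documents support:

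- **That reportable events will be missed.** The central review of SAEs stands between the site rating and any report, and the documents do not show a report turning on the rating alone.
- **That correcting the definition can only raise the number of events counted as related.** No current threshold for related is stated. If Unlikely related, which concedes some possibility, is now being counted, a stated cut-point could lower the number.
- **That the cut-point belongs at Possibly related.** That depends on a regulation whose text is not in the documents.
- **That the gap can be expressed as a share of cases covered.** Because Probably related carries two conditions, a partition by the strength of the alternative cause alone misclassifies case C. The number of affected events cannot be estimated.

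**What to change.** In 16.1.4, redefine Possibly related as an AE with a reasonable, more than remote possibility of being caused by study drug that does not meet the criteria for Probably or Definitely related, whether or not an alternative cause is equally or more plausible. This takes in cases A, B and C and restores the order of the levels. Match the AE-form instructions to it.

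In the same change, state in 16.3 which levels count as related, consistent with the regulation cited there. The choice of cut-point is for the sponsor.

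The cost is one definition, one sentence and matching form instructions. The downside is that some events may be coded differently than they would be now, in a direction that the documents do not allow one to determine.
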